Adult patients with advanced osteoarthritis who are scheduled to undergo total knee replacement surgery, meeting all inclusion/exclusion criteria, will be approached by a study team member. The team member will review the study with the patient and, if appropriate, obtain their consent to participate in the study.

b. Inclusion and Exclusion Criteria

Inclusion:

- ≥ 18 years of age
- Radiographic evidence of advanced knee osteoarthritis
- Knee pain
- Scheduled to undergo a total knee replacement

Exclusion:

- < 18 years of age
- Unable to provide written consent
- Known allergy to fish or astaxanthin
- Pregnant and/or breastfeeding
- Received a corticosteroid injection within 3 months of initiating treatment with astaxanthin or placebo
- Currently taking immunosuppressant drugs or drugs which act as a 5-alpha reductase inhibitor

- History of any autoimmune condition
- Known autoimmune etiology for arthritis (e.g. Rheumatoid or Psoriatic arthritis)

c. Number of Subjects

160 total patients included in this study, 80 per treatment arm.

d. Study Procedures

Once patients have been enrolled in the study, they will complete a Patient Reported Outcome Measurement Information System (PROMIS) Physical Function and Pain Interference assessment. This assessment will be administered on an iPad by clinic or research staff and data will be recorded in REDCap.

Participants will be randomized to receive a daily oral regimen of either astaxanthin (12mg) or placebo over a 6-week period prior to surgery. Patients will record compliance with taking the supplement via a log provided to them at the time of consent.

Research staff will call participants biweekly over the 6-week period to assess pain score, supplement compliance and record any side effects from the astaxanthin or placebo.

On the day of surgery, participants will again complete the PROMIS Physical Function and Pain Interference assessment when they arrive at the hospital. This assessment will be administered on an iPad by clinic or research staff and data will be recorded in REDCap.

At the time of surgery, following sedation, an aliquot of synovial fluid will be collected from the affected knee by the orthopedic surgeon performing the surgery. Obtained samples will be analyzed to measure levels of pro- and anti-inflammatory cytokines and chemokines.

e. Study Timelines

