Following IRB approval, we will begin prospectively enrolling eligible patients in this study. Currently, [name] treats approximately 50 patients in clinic per week, with nearly 50% suffering from knee osteoarthritis. Overall, he performs 2-6 knee replacements for advanced osteoarthritis per week. Given the high volume of patients treated by [name] with advanced osteoarthritis who will ultimately undergo total knee replacement surgery, we expect to achieve complete enrollment of 160 participants in a 10-12-month period. Additional orthopedic surgeons may be included to increase enrollment, if necessary.

Following the completion of participant enrollment and data collection, the

obtained results will be reviewed and statistically analyzed over a 2-month period.

f. Study Endpoints

Pain interference and physical function between the astaxanthin and placebo control group as measured by PROMIS Physical Function and Pain Interference assessments prior to beginning astaxanthin or placebo treatment regimen and just prior to surgery.

Inflammatory profiles of post-treatment synovial fluid from the astaxanthin and placebo control group as measured by levels of pro- and anti-inflammatory chemokines and cytokines.

g. Medication Treatment protocol

Pre-Operatively:

12mg Astaxanthin or placebo once daily for 6 weeks prior to surgery

h. Data Collection/Banking

All data will be stored on a password-protected, encrypted spreadsheet. Only members of the study team will have access to this information.

Participants will be given a unique study ID and a separate password-protected document will be created linking patients to their study ID.

Data recorded via PROMIS and phone surveys will be stored on the Prisma Health REDCap sever, a secure web application for managing research databases.

Synovial fluid samples will be stored in a -80C freezer in a locked laboratory and will only be accessible to members of the study team. Samples will be labeled with study IDs given to participants.

i. Statistical Analysis

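### Does the 10-12-month enrolment forecast, which one surgeon's volume may not support, put the planned 160 participants at risk?

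*Combined protocol and SAP*

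**What the plan says.** Section 5.c sets the size: "160 total patients included in this study, 80 per treatment arm". Section 5.e forecasts that "we expect to achieve complete enrollment of 160 participants in a 10-12-month period". It rests this on one surgeon, who "treats approximately 50 patients in clinic per week, with nearly 50% suffering from knee osteoarthritis", and adds that "he performs 2-6 knee replacements for advanced osteoarthritis per week". It then allows for slower accrual: "Additional orthopedic surgeons may be included to increase enrollment, if necessary". The statistical work is scheduled for the two months after enrolment and data collection are complete; no calendar date triggers it.

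Three other passages bear on the supply of patients.

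- Section 5.b admits only patients who meet the criterion "Scheduled to undergo a total knee replacement". Its exclusions include "Received a corticosteroid injection within 3 months of initiating treatment with astaxanthin or placebo", immunosuppressants, 5-alpha reductase inhibitors, autoimmune history, and fish or astaxanthin allergy.
- Section 5.g specifies "12mg Astaxanthin or placebo once daily for 6 weeks prior to surgery", so patients must be consented some weeks ahead of the operation.
- Section 4 says that two orthopaedic surgeons lead the team. Only one surgeon's volume is quoted anywhere.

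**The concern.** The forecast is presented as following from the surgeon's volume. Because only patients already booked for knee replacement qualify, long-run enrolment cannot exceed the rate of operations, and the larger clinic figure does not lift that ceiling. Exclusions, refusals and the need for a six-week lead before surgery all reduce the share who can enter, and the protocol puts no figure on any of them. The lower part of the quoted range cannot reach 160 in a year even if every patient enrols.

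If the trial then stopped on its stated calendar, it would have fewer than 80 per arm and less precision than 160 patients would give. Extra surgeons are mentioned only as an option, with no number, volume or trigger.

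**Working it through.** **Inputs.** Target 160 (5.c); period 10-12 months (5.e); 2-6 knee replacements a week (5.e). The midpoint of 4 a week is a derived value that the protocol does not state. At 52/12 weeks a month, 10-12 months is 43.3-52 weeks.

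**Rate needed.** 160/52 = 3.08 and 160/43.3 = 3.69 enrolments a week.

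**Operations available and share needed.** Operations = rate × weeks; share = 160/operations; months if every patient enrols = (160/rate)/(52/12).

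| Sustained rate | Operations in 10-12 months | Share that must enrol | Months to 160 at 100% |
|---|---|---|---|
| 2 a week | 87-104 | 154-185% | 18.5 |
| 3 a week | 130-156 | 103-123% | 12.3 |
| 4 a week | 173-208 | 77-92% | 9.2 |
| 6 a week | 260-312 | 51-62% | 6.2 |

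The stated period is therefore reproduced only if the surgeon's average is towards the middle or top of the range and the enrolled share is high.

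**Sensitivity to the calendar.** At 4 a week, counting four weeks a month gives 83-100%. Subtracting six weeks gives 87-107%, but that applies only if the operations must also fall inside the window. The forecast concerns enrolment, which happens before the six weeks of treatment.

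**Sensitivity to the enrolled share.** The protocol gives no share, so 30-80% is an assumption. Months = 160/(4 × share)/(52/12) at 4 a week:

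- 30%: 30.8 months
- 40%: 23.1 months
- 50%: 18.5 months
- 60%: 15.4 months
- 80%: 11.5 months

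The top of this range meets the stated period. At 6 a week, 50% gives 12.3 months and 60% gives 10.3 months.

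**Effect of a second surgeon (illustration).** If a second surgeon also performed 4 a week, which is an assumption, the share needed would be 160/(8 × 52) = 38% to 160/(8 × 43.3) = 46%.

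**The feared loss of precision.** At 4 a week and an assumed 50% enrolled, 12 months yields 4 × 52 × 0.5 = 104 patients, or 52 per arm. For a two-sample t-test with 80% power at two-sided 0.05, the detectable difference is 0.446 SD with 80 per arm and 0.555 SD with 52. That comparison describes this trial only if enrolment closes at 12 months. Section 5.c gives a fixed number, and 5.e places the analysis after enrolment is complete. Neither section contains a closing date.

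**The case for a change.** The strongest case for a change is that section 5.e draws an explicit inference that its own figures do not support. The low end of the range fails at any enrolled share, and the midpoint needs nearly every surgical patient despite several exclusions and a placebo arm. The clause on additional surgeons acknowledges the risk without quantifying it. A backlog of patients already booked could help early on, but none is described. The correction is only wording, and the protocol never says outright whether a slow trial would continue to 160 or stop on the calendar.

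Part of this stands. The arithmetic is right, the forecast is optimistic on the quoted volume, and the assumed enrolled share is missing.

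The rest does not carry a change. A range of 2-6 a week reads naturally as week-to-week variation, so a sustained 2 a week for a year is a scenario the protocol does not assert. The required 3.1-3.7 a week sits inside the range. Any shortfall would show in the weekly counts, so leaving extra surgeons optional does not delay its discovery. On the question of stopping or continuing, the text that exists points to continuing: the number is fixed and the analysis waits for it. Replacing 10-12 months with, say, 15-23 months would exchange one unsupported forecast for another, because the 40-60% share behind it is also assumed.

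**Conclusion.** The concern is correct as a remark on feasibility, but it does not call for a change to the plan. On one surgeon's volume, 160 in 10-12 months needs 51-62% of surgical patients at 6 a week and 77-92% at 4 a week, and cannot be reached at a sustained 2 a week. The likely consequence is a longer enrolment period, or earlier use of the surgeons the protocol already permits. With an assumed 30-80% enrolled at 4 a week, enrolment would take between 30.8 and 11.5 months.

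The sample size, the comparisons and the precision at 80 per arm stay as planned. This rests on reading 160 as the point at which enrolment ends, which is what sections 5.c and 5.e support. The loss to 52 per arm would need a 12-month closure and a 50% share, and the protocol states neither. What is missing is planning detail that the study team can supply from its own accrual counts, and adding it would change no result.

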This prospective, blinded, randomized, placebo-controlled pilot study will evaluate the effect of astaxanthin in reducing inflammation, controlling pain, and improving physical function in patients with advanced knee osteoarthritis awaiting total joint replacement surgery. Levels of pro- and anti-inflammatory cytokines and chemokines will be measured following the completion of a daily oral regimen of astaxanthin vs. placebo. Additionally, patient-reported outcome measurements assessing physical function and pain interference will be obtained prior to and following completion of treatment allowing for a comparison between treatment groups. Study outcomes will provide evidence to support astaxanthin supplementation as a cost-effective, added strategy for symptom management in patients with advanced osteoarthritis and will lay the foundation to seek additional federal funding to conduct a large-scale clinical trial to further establish the efficacy of this treatment strategy.

2. Objectives / Research Aims

The goals of this study are to:

- a. Determine the effect of astaxanthin on pain control and physical function in patients with osteoarthritis who are scheduled to undergo a total knee replacement surgery.
- b. Determine the effect of astaxanthin on inflammatory synovial markers in patients with osteoarthritis who are scheduled to undergo a total knee replacement surgery.

3. Setting

This study will take place at Prisma Health Orthopedics clinic facilities and Prisma Health Baptist Hospital.

4. Resources Available

Documentation will be comprised of a thorough history and physical, clinical progress notes, operative reports, anesthesia reports, and post-operative progress notes available on the EPIC EMR as well as patient reported outcome measurements collected via PROMIS surveys and stored on the Prisma Health REDCap server, a secure data collection platform.

Two fellowship trained orthopaedic surgeons will lead the research team.

The research team will be comprised of practicing orthopaedic surgeons, the Chair of the Department of Pathology, Microbiology, and Immunology, resident orthopaedic surgeons in training, medical students, clinical nursing staff, and research assistants.

5. Study Design

This will be a prospective, double-blinded, randomized, placebo-controlled pilot study.

a. Recruitment Methods

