PROMIS assessments will be completed at two time points: prior to beginning the astaxanthin or placebo treatment regimen and just prior to surgery, at the time of completing the treatment regimen. A paired t-test will be performed to detect differences in the before and after measurements per group. These differences will then be compared for patients in the astaxanthin arm vs. placebo arm to determine if participants receiving astaxanthin report a significant difference in pain and physical function ability following completion of the treatment regimen.

Synovial fluid will be collected in heparinized tubes at the time of surgery. A quantitative analysis of immune cell infiltration will be performed from the synovial fluid collected, using a hematology analyzer. This will provide total and

differential WBC counts. Further studies will be done to estimate the cytokine and chemokine levels in synovial fluid. Statistical analysis will be performed and a p value < 0.05 between groups will be considered statistically significant.

j. Data Management

Data will be maintained on a secure password protected server. Only IRB authorized research study members can access this information. The researchers involved in this study commit to handle all information with care and to protect research subjects' identity. The data collected will be kept for at least three years after publication and then destroyed in accordance with the hospital and federal guideline. Participants will be given a unique study ID and a separate password-protected document will be created linking patients to their study ID. No PHI will be disclosed during statistical analysis or subsequent presentations or publications.

k. Confidentiality

All study related data activities will take place on password-protected network supported by the home hospital institution. Study team has been educated and agrees to uphold the hospital and federal confidentiality laws.

l. Provisions to Monitor the Data to Ensure the Safety of Subjects

Data will be maintained on a secure server with password protection. Study data and signed consent documents will be stored in a locked office in Prisma Health Orthopedics. Only authorized research members of this study can access this information. The researchers involved in this study commit to handle all information with care and to protect research subjects' identities.

6. Risks to Subjects

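### The PROMIS arm comparison names no between-arm model; adjusting for the baseline score already collected would in general be more precise at almost no cost

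*Combined protocol and SAP*

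**What the plan says.** The PROMIS analysis is set out in the first paragraph of section 5.i. It has two steps. Within arms: "A paired t-test will be performed to detect differences in the before and after measurements per group". Between arms: "These differences will then be compared for patients in the astaxanthin arm vs. placebo arm", with the stated purpose "to determine if participants receiving astaxanthin report a significant difference in pain and physical function ability following completion of the treatment regimen". The second step answers the research question. It serves aim (a) in section 2 and the first endpoint in section 5.f, "Pain interference and physical function between the astaxanthin and placebo control group as measured by PROMIS Physical Function and Pain Interference assessments". Yet the only test named for PROMIS is the within-arm one.

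The only significance criterion closes the following paragraph, on synovial fluid: "Statistical analysis will be performed and a p value < 0.05 between groups will be considered statistically significant". It does not say which outcomes it covers or whether tests are one- or two-sided.

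Sections 5.d and 5.i have both PROMIS scores measured at enrolment, before treatment starts, and again on the day of surgery. Section 5.c sets the size: "160 total patients included in this study, 80 per treatment arm". No justification for that number is given, and no correlation, SD, target difference or power appears anywhere.

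**The concern.** A change score does use the baseline, but it fixes the baseline slope at 1: each participant's whole baseline value is subtracted from the follow-up value. ANCOVA estimates the slope from the data. When the true slope is below 1, as is usual with an imperfectly repeatable questionnaire score, subtracting the whole baseline adds noise to the treatment comparison.

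The within-arm paired tests do not help here. They describe change over about six weeks in each group and do not bear on astaxanthin versus placebo.

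What is at stake is the precision of the two PROMIS treatment effects. According to the opening summary, this pilot "will lay the foundation to seek additional federal funding to conduct a large-scale clinical trial", so intervals wider than the data allow would carry over into the planning of the next study. Leaving the model unnamed also leaves the choice between an adjusted and an unadjusted comparison open until the data have been seen.

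**Working it through.** There is no planned power or precision figure to reproduce, so the check compares the two estimators at the planned size.

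**Inputs from the document:** 80 per arm, N = 160 (5.c); both PROMIS scores at both visits (5.d, 5.i).

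**Assumed, because not stated:** complete data; two-sided 5% level; correlation rho between baseline and follow-up from 0.3 to 0.9; ratio k of follow-up SD to baseline SD of 0.8, 1 or 1.3; true differences of 0.2 to 0.4 score SD for power.

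**Step 1: per-participant variances.** With baseline SD s0 and follow-up SD s1:
- change score: s0² + s1² − 2·rho·s0·s1
- ANCOVA: s1²(1 − rho²)
- change score minus ANCOVA: s0² − 2·rho·s0·s1 + rho²·s1² = (s0 − rho·s1)²

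The difference is never negative, and it is zero only when rho·k = 1.

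**Step 2: cost of estimating the slope.** This multiplies the ANCOVA variance by 1 + 1/(N − 4) = 1 + 1/156 = 1.0064. The variance ratio, ANCOVA over change score, is therefore

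k²(1 − rho²) / (1 + k² − 2·rho·k) × 1.0064,

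which at k = 1 becomes (1 + rho)/2 × 1.0064. For rho = 0.5 this is 0.75 × 1.0064 = 0.755.

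**Step 3: interval width, matching sample size and power at k = 1.** The half-width is t × sqrt(V × 2/80), in score SDs. For the change score, V = 2(1 − rho) on 158 df. For ANCOVA, V = (1 − rho²) × 1.0064 on 157 df. For rho = 0.5, sqrt(1 × 2/80) = 0.158 and sqrt(0.755 × 2/80) = 0.137, giving half-widths of 0.312 and 0.271. The matching size is 80 divided by the ratio. Power uses the noncentral t with the same V and df.

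| rho | Variance ratio | Half-width, change score → ANCOVA | CI narrower by | Change-score n per arm to match ANCOVA with 80 | Power at 0.3 SD, change score → ANCOVA |
|---|---|---|---|---|---|
| 0.3 | 0.654 | 0.370 → 0.299 | 19.1% | 122 | 35.7% → 50.4% |
| 0.5 | 0.755 | 0.312 → 0.271 | 13.1% | 106 | 47.1% → 58.3% |
| 0.7 | 0.855 | 0.242 → 0.224 | 7.5% | 94 | 68.2% → 74.9% |
| 0.8 | 0.906 | 0.198 → 0.188 | 4.8% | 88 | 84.7% → 88.0% |
| 0.9 | 0.956 | 0.140 → 0.137 | 2.2% | 84 | 98.8% → 99.1% |

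At rho = 0.5 the power gain is 24.2% → 30.4% for a true difference of 0.2 SD and 71.0% → 82.5% for 0.4 SD.

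**Step 4: unequal SDs.** Variance ratios for rho = 0.3, 0.5, 0.7, 0.8 and 0.9:
- k = 0.8: 0.505, 0.575, 0.632, 0.644, 0.612
- k = 1.3: 0.810, 0.918, 0.997, 1.004, 0.923

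If follow-up scores are more spread out than baseline scores, the gain can vanish. At k = 1.3 and rho = 0.8 there is a trivial loss.

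**Step 5: worst case.** When rho·k = 1 the ratio is 1.0064, that is 0.64% more variance and an interval about 0.3% wider. At k = 1, ANCOVA is worse only above rho = 2/1.0064 − 1, about 0.987. At k = 1.3 it is worse only for rho of about 0.71 to 0.82.

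**Step 6: simulation, 20,000 trials per setting.** At k = 1 the simulated ratios for the five correlations were 0.656, 0.750, 0.857, 0.912 and 0.958. At k = 1.3 they were 0.919, 0.998 and 1.004 for rho 0.5, 0.7 and 0.8. At rho·k = 1 the ratio was 1.006. All are close to the formula. On one simulated data set, ANCOVA on the change and ANCOVA on the follow-up score gave the same estimate and standard error (0.6351, SE 0.1165).

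**The case against.** The strongest reply is that nothing here is wrong. The change-score comparison is unbiased under randomisation, it fits an endpoint measured at two visits, and preferring ANCOVA is a choice between two valid estimators. That stands, and it is why this is called a free improvement.

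Second, the text does not say the comparison will be unadjusted. Because ANCOVA on the change gives the same treatment effect as ANCOVA on the follow-up score, an adjusted comparison of differences would be compatible with the wording. This also stands: the efficiency loss is conditional on the plain reading. But it is equally an argument for naming the model, since the current sentence permits either.

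Third, every figure rests on assumed inputs, and the plausible range runs from about half the variance to no gain at all. The document gives no support for the low correlations at which the gain is largest. The figures show a general property of the method at this sample size and do not measure harm to this trial. What survives is the asymmetry: a possible gain of several to many percent against a worst-case loss of 0.64% in variance.

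Fourth, the 0.05 criterion is the last sentence of 5.i and names no outcome, so it can be read as covering PROMIS too. That is a fair reading, and only the missing sidedness is clear. Likewise, the plan nowhere presents the paired tests as evidence of a treatment effect. Both are side points, and the recommendation does not depend on them.

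**Conclusion.** The point holds as a free improvement that should be made. The plan names no between-arm model for PROMIS, and the plain reading is an unadjusted change-score comparison, which is valid but in general less precise than ANCOVA. With equal SDs and correlations of 0.3 to 0.9, ANCOVA has 0.654 to 0.956 of the change-score variance. At a correlation of 0.5 the gain is worth about 106 − 80 = 26 extra participants per arm. These sizes assume complete data in 80 per arm. Since the documents give neither the correlation nor the SDs, the actual gain is unknown and may be small.

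**What to change.** In section 5.i, replace the sentence on comparing the differences between arms with:

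> For each PROMIS score the treatment effect is the between-arm difference in the pre-surgery score, estimated by ANCOVA with arm and baseline score as covariates, and reported with its 95% confidence interval and two-sided p-value (alpha 0.05).

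Keep the paired t-test sentence and add:

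> Within-arm changes and paired t-tests are descriptive only and are not evidence of a treatment effect.

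If the team prefers to report change, the same model with the change as outcome gives the same treatment effect, provided baseline stays in as a covariate.

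The cost is wording only, apart from the small worst-case loss shown above. This wording does not settle how missing day-of-surgery scores are handled, or multiplicity across the two PROMIS scores. Both need their own sentences.
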